# Appendix J. Two-parameter BLRM Design

A two-parameter Bayesian Logistic Regression Model (BLRM) is used to guide dose exploration. The MTD target Toxicity Probability Interval (TPI) for DLT is (0.20, 0.33] and TPIs of (0.33, 0.60] and (0.60, 1.00] are defined as excessive and unacceptable, respectively. The design seeks to identify a dose most likely to have a DLT rate in the target TPI, but with overdose control that limits the possibility the dose has an excessive or unacceptable DLT rate (Babb et al, 1998). The probability of a DLT at dose level di is assumed to follow a Bernoulli distribution with probability pi where the logit of pi increases linearly with the log of the standardized dose in the following 2-parameter logistic model:

 $\log [p_i / (1-p_i)] = logit(p_i) = log[a] + exp( log[b]) log (d_i / d_{ref})$ 

where a and b are random variables and  $d_{ref}$  is 1 of the planned dose selected as the reference dose.

A bi-variate normal prior distribution (Neuenschwander et al, 2008) was selected for theta = (log a, log b) where the probability that the true DLT rate is  $\leq$  0.40 at the lowest planned dose is 0.90 and the probability the true DLT rate is  $\leq$  0.05 at the reference dose is 0.05. These values were selected such that pi is 0.01 for the starting dose and 0.40 for the reference dose ( $\mu$  µg). Subsequent model runs may adjust the reference dose level lower or higher depending on the true DLT dose levels.

The operating characteristics of the two-parameter BLRM design were evaluated via simulation using EAST version 6.4.1. The cohort size was fixed to 3 or 4 subjects. All simulated studies start with the multiple subject cohorts. The initial multiple subject dose level is  $\mu$ g and subsequent doses were selected based on the following rules:

After each cohort, the next dose is the one with the highest probability of the target TPI, but with a less than 0.40 probability of an excessive or unacceptable TPI.

Dose exploration will continue until any of the following events.

- The highest planned dose level is determined to be safe and tolerable (minimum of 6 treated subjects)
- An MTD is identified where BLRM repeats the recommendation of a dose level (minimum of 6 treated subjects)
- If fewer than 6 subjects are treated at the MTD/RP2D, additional subjects may be enrolled to confirm safety and tolerability.

Operating characteristics are described below.

#### **Operating characteristics**

The 6 planned dose levels (unit:  $\mu$ g) for the multiple subject cohorts were considered: in these simulations. This assumes that the single subject cohorts execute without any safety issue.

The design was evaluated for 3 possible dose-response scenarios: "Low", "Mid", and "High" MTD. Table 20 shows the dose level and true probability of DLT for each scenario used in the simulated studies estimating the MTD. Table 21 reports the operating characteristics from 10,000 simulated studies estimating the MTD when the target TPI is (0.20, 0.33]. Table 22 reports the operating characteristics from 10,000 simulated studies a 3+3 design.

# Table 20. True Probability of DLT by Scenario for Simulated Studies EstimatingMTD

Dose Level (µg)						
MTD Scenario						
High	0.02	0.08	0.12	0.15	0.18	0.33
Mid	0.04	0.12	0.18	0.3	0.4	0.5
Low	0.06	0.18	0.3	0.45	0.5	0.6

DLT = dose-limiting toxicity; MTD = maximum tolerated dose.

MTD Scenario High		Mid		Low		
			4 subjects per cohort			
Number of Subjects	24	18	24	18	20	15
Median (IQR)	(20 to 28)	(1 to 3)	(20 to 24)	(15 to 18)	(16 to 24)	(12 to 18)
Number of DLTs	3	2	4	3	5	3
Median (IQR)	(2 to 4)	(1 to 3)	(3 to 5)	(2 to 4)	(4 to 6)	(3 to 4)
Proportion of DLT (%)	13	10	20	20	25	25
Median (IQR)	(10 to 17)	(6 to 14)	(15 to 23)	(14 to 22)	(20 to 29)	(20 to 28)
Percentage of studies recommending dose with DLT probability of:						
≤ 10%	2.2	2.3	2.0	2.0	6.0	7.9
> 10% and ≤ 20%	83.2	87.9	37.7	35.0	25.7	20.8
> 20% and ≤ 33%	14.6	9.5	49.9	50.7	49.1	44.7
> 33%	0	0	10.4	12.3	22.2	26.6
Probability of identifying MTD with DLT probability of >15% and ≤ 33%	54.6	53.2	81.8	77.8	74.8	65.5

# Table 21. Operating Characteristics by Scenario for Simulated Studies Estimating
the MTD When the Target TPI is (0.20, 0.33)

DLT = dose-limiting toxicity; IQR = interquartile range; MTD = maximum tolerated dose; TPI = toxicity probability interval.

Table 22.	Operating Characteristics by Scenario for Simulated Studies Estimating
	the MTD Using a 3+3 Design

	· · J	0	
MTD Scenario	High	Mid	Low
Number of Subjects	21	18	15
Median (IQR)	(18 to 24)	(15 to 21)	(12 to 18)
Number of DLTs	3	3	3
Median (IQR)	(2 to 3)	(2 to 4)	(2 to 4)
Proportion of DLT (%)	14	19	22
Median (IQR)	(10 to 17)	(17 to 22)	(17 to 25)
Percentage of studies reco	mmending dose with	DLT probability of:	
≤ 10%	19.4	16.0	30.4
> 10% and ≤ 20%	57.7	55.8	38.7
> 20% and ≤ 33%	0	20.53	24.5
> 33%	22.53	7.4	6.1
Probability of identifying MTD with DLT probability of >15% and $\leq$ 33%	25.0	54.8	63.2

DLT = dose-limiting toxicity; IQR = interquartile range; MTD = maximum tolerated dose

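### Table 22 shows the 3+3 design choosing a dose above 33% DLT in 22.53% of High-scenario studies, where no such dose exists; one Table 21 column adds to 103.0%

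*Protocol*

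**What the plan says.** Appendix J of the protocol sets the categories: "The MTD target Toxicity Probability Interval (TPI) for DLT is (0.20, 0.33", closed with a square bracket, so 0.33 itself is on target and excessive toxicity starts above it.

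Table 20 gives the true DLT rates used in the simulations, six doses per scenario:

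- "High 0.02 0.08 0.12 0.15 0.18 0.33"
- "Mid 0.04 0.12 0.18 0.3 0.4 0.5"
- "Low 0.06 0.18 0.3 0.45 0.5 0.6"

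Tables 21 and 22 then report, from 10,000 simulated studies each, how often the recommended dose falls in each band of true DLT rate. Table 21 (BLRM) has two columns per scenario, and its top band reads "> 33% 0 0 10.4 12.3 22.2 26.6". Table 22 (3+3) has one column per scenario, and its top band reads "> 33% 22.53 7.4 6.1". In the band for >20% to ≤33%, the High entries are 14.6 and 9.5 in Table 21 and 0 in Table 22.

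The Table 21 title writes the interval as "Target TPI is (0.20, 0.33" followed by a round bracket, which would exclude 0.33.

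**The concern.** The two tables put the same High-scenario dose in different bands. Table 21 counts the 0.33 dose as on target; Table 22 counts it as an overdose. Only the first agrees with the definition in Appendix J and with the row labels of both tables.

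These tables are the only stated operating characteristics of the dose-finding design, and 3+3 is its only benchmark. As printed, High is the one scenario in which the BLRM appears to select overly toxic doses less often than 3+3 (0 against 22.53), and the one in which its bottom-row lead over 3+3 is largest for both cohort sizes. If the entry is in the wrong row, the overdose difference disappears and most of that lead goes with it.

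Two entries in Table 21 also look wrong by inspection. One column of mutually exclusive percentages exceeds 100, and one interquartile range does not contain its median.

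**Working it through.** **Column identity in Table 21.** The cohort-size labels are partly lost in the text available to me. The sample-size entries identify the columns: medians and quartiles such as 24 (20 to 28) and 20 (16 to 24) are multiples of 4, and 15 (12 to 18) are multiples of 3. The columns therefore alternate 4 and 3 per cohort.

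**Step 1: High scenario, top band.** The largest High rate is 0.33, and 0.33 is not greater than 0.33. The entry must be 0 under any design. Table 21 has 0 and 0; Table 22 has 22.53.

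**Step 2: is 22.53 the 0.33 dose in the wrong row?** The protocol does not say which 3+3 variant was simulated. In the simplest one, a dose with DLT rate p is passed with 0/3, or with 1/3 followed by 0/3:

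pass(p) = (1−p)³ × [1 + 3p(1−p)²]

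For the High rates this gives 0.9954, 0.9369, 0.8715, 0.8138, 0.7516 and 0.4344.

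- Passing the first five doses: the product of the first five terms = 0.497.
- Recommending the 0.33 dose: 0.497 × 0.4344 = 21.6%.
- Recommending the 0.18 dose: 0.497 × (1 − 0.4344) = 28.1%.

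Exact enumeration of three variants gives the results below. A has no expansion to 6 before the MTD is declared. B requires 6 at a declared MTD, but 3 suffice at the top dose. C requires 6 in both cases.

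| Quantity (3+3), % | A | B | C | Table 22 |
|---|---|---|---|---|
| High, above 33% | 0 | 0 | 0 | 22.53 |
| High, 0.33 dose | 21.6 | 21.6 | 17.8 | (0 in its row) |
| High, 0.18 dose alone | 28.1 | 26.3 | 29.9 | not shown |
| High, >15% to ≤33% | 49.7 | 47.9 | 47.7 | 25.0 |
| Mid, >15% to ≤33% | 54.5 | 54.3 | 54.4 | 54.8 |
| Low, >15% to ≤33% | 64.0 | 63.6 | 63.6 | 63.2 |

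Variant B also gives 7.8 (Mid) and 6.1 (Low) above 33%, against 7.4 and 6.1 printed. In simulation it matches Table 22's medians and quartiles for subjects and DLTs in all three scenarios. Mid and Low therefore reproduce closely, and High does not.

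**Step 3: the bottom row for High.** If 25.0 already included the 0.33 dose, the 0.18 dose would account for only 25.0 − 22.53 = 2.47%, against 26.3 to 29.9% above. So 25.0 is close to the 0.18 dose alone. Including the 0.33 dose gives 25.0 + 22.53 = 47.53.

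**Step 4: effect on the comparison** (BLRM with 4 / 3 per cohort against 3+3):

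| Band, % | Scenario | BLRM | 3+3 printed | 3+3 re-binned |
|---|---|---|---|---|
| >15% to ≤33% | High | 54.6 / 53.2 | 25.0 | about 47.5 |
| | Mid | 81.8 / 77.8 | 54.8 | unchanged |
| | Low | 74.8 / 65.5 | 63.2 | unchanged |
| >20% to ≤33% | High | 14.6 / 9.5 | 0 | 22.53 |
| | Mid | 49.9 / 50.7 | 20.53 | unchanged |
| | Low | 49.1 / 44.7 | 24.5 | unchanged |
| above 33% | High | 0 / 0 | 22.53 | 0 |
| | Mid | 10.4 / 12.3 | 7.4 | unchanged |
| | Low | 22.2 / 26.6 | 6.1 | unchanged |

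The BLRM's bottom-row lead in High is 54.6 − 25.0 = 29.6 and 53.2 − 25.0 = 28.2 points as printed. Re-binned, it is 54.6 − 47.53 = 7.1 and 53.2 − 47.53 = 5.7.

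**Step 5: column sums.** Table 21: 100.0, 99.7, 100.0, 100.0, 103.0, 100.0. Table 22: 99.63, 99.73, 99.7. The 103.0 is Low with 4 per cohort: 6.0 + 25.7 + 49.1 + 22.2. In the Low scenario the bottom row must equal the sum of the two middle rows, because only the 0.18 and 0.3 doses qualify. It does: 25.7 + 49.1 = 74.8. The 3.0-point excess therefore most likely sits in the 6.0, the 22.2, or both, and the documents do not show which. If all of it is in the top band, that entry is 22.2 − 3.0 = 19.2.

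**Step 6: the interquartile range.** Table 21, High, 3 per cohort, gives a median of 18 subjects with quartiles 1 to 3. That is impossible, and it equals the DLT-count range two rows below.

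**The case against.** The best counter-argument is that little depends on this. Table 22 describes a design the trial does not use, no decision rule draws on it, and the protocol never claims in words that the BLRM is superior. The SAP does not reproduce Tables 20 to 22. It records early discontinuation (Section 1) and drops the summary of toxicity-interval probabilities (Section 10). The less favourable Mid and Low overdose figures are already in print, and the BLRM keeps its bottom-row lead in every scenario. All of this stands. It limits the consequence to the accuracy of the design record and any later reuse of the tables.

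The replication is also only approximate. Under variant B, 22.53 against 21.6 is about 2.3 Monte Carlo standard errors, and 25.0 against 26.3 is about 3 (standard error 0.44 at 10,000 studies). Hence 47.5 is an inference. The zero in the top band needs no simulation.

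Could 0.33 stand for one third? Then Table 21's High columns would be wrong instead, so the tables conflict either way. A PDF-reading fault is unlikely for the 22.53, because the 25.0 in a separate row carries the same omission. It cannot be excluded for the range of 1 to 3.

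The round bracket in the Table 21 title did not cause the error, since Table 21 itself bins 0.33 correctly. It is a notation slip only.

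**Conclusion.** The point holds. By the protocol's own definitions, the High entry of 22.53 above 33% in Table 22 is impossible, and it contradicts Table 21's treatment of the same dose. The 103.0% column and the interquartile range that excludes its median are wrong as they read.

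The correction to 3+3's bottom-row figure in High, from 25.0 to about 47.5, assumes that 22.53 is the 0.33 dose and that 25.0 leaves it out. Three 3+3 variants support this with 47.7 to 49.7%. On that basis the BLRM's lead in High shrinks to about 6–7 points, and 3+3 moves ahead in High for >20% to ≤33%. In no scenario does the BLRM then select overdoses less often: it ties at 0 in High and is higher in Mid and Low. The Low conclusion survives the column-sum doubt, since 19.2 still exceeds 6.1.

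This should be corrected, but it is a reporting error. It does not alter dose escalation, stopping boundaries or sample size.

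**What to change.** Regenerate Tables 21 and 22 from the simulation output with one rule, counting 0.33 in the ≤33% bands as Appendix J defines it. Take three items from that output rather than adjusting them by hand: the High column of Table 22, the Low 4-per-cohort column of Table 21, and the sample-size quartiles for High with 3 per cohort. Any BLRM versus 3+3 comparison should then use the corrected tables for all three scenarios.

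Two small additions would help. Write the interval as (0.20, 0.33] in the Table 21 title and in the SAP's definition of MTD (Section 5), which also leaves it open at 0.33. State which 3+3 variant was simulated.

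If the output has been kept, the cost is a re-tabulation and a few text edits; otherwise the simulations must be rerun. The design, decision rules and sample size stay as they are.

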# Appendix K. Cairo-bishop Clinical Tumor Lysis Syndrome Definition and Grading

CTCAE version 4.0 classifies TLS in grade 3 (present), grade 4 (life threatening consequences; urgent intervention indicated) and grade 5 (death). Presence of TLS is not clearly defined by CTCAE version 4.0. Cairo and Bishop developed a system for defining and grading TLS based on Hande-Garrow classification of laboratory or clinical TLS (Coiffier et al, 2008). For this trial the Cairo-Bishop classification will be used to define presence of TLS, ie, presence of laboratory TLS (see Table 23) and clinical TLS (see Table 24) including grading as detailed below

Based on the Cairo and Bishop system, laboratory TLS is present when levels of 2 or more serum values of uric acid, potassium, phosphorus, or calcium are more than or less than normal at presentation or if they change by 25% within 3 days before or 7 days after initiation of treatment (Table 23).

Element	Value	Change from Baseline
Uric acid	≥ 476 µmol/L or 8 mg/dL	25% increase
Potassium	≥ 6.0 mmol/L or 6 mg/L	25% increase
Phosphorus	≥ 2.1 mmol/L for children or ≥ 1.45 mmol/L for adults	25% increase
Calcium	≤ 1.75 mmol/L	25% decrease

 Table 23. Cairo-bishop Definition of Laboratory Tumor Lysis Syndrome

Note: Two or more laboratory changes within 3 days before or 7 days after cytotoxic therapy will constitute laboratory TLS.

Clinical TLS requires the presence of laboratory TLS in addition to 1 or more of the following significant complications: renal insufficiency, cardiac arrhythmias/sudden death, and seizures (Table 24). The grade of clinical TLS is defined by the maximal grade of the clinical manifestations as detailed in Table 24.

Grade	Creatinine a, b	Cardiac Arrhythmia a	Seizure a
0	≤ 1.5 x ULN	None	None
1	1.5 x ULN	Intervention not indicated	
2	> 1.5 – 3.0 x ULN	Non urgent medical intervention indicated	One brief, generalized seizure; seizure(s) well controlled by anticonvulsants or infrequent focal motor seizures not interfering with ADL
3	> 3.0 – 6.0 x ULN	Symptomatic and incompletely controlled medically or controlled with device (eg, defibrillator)	Seizure in which consciousness is altered; poorly controlled seizure disorder; with breakthrough generalized seizures despite medical intervention
4	> 6.0 x ULN	Life-threatening (eg, arrhythmia associated with CHF, hypotension, syncope, shock)	Seizure of any kind which are prolonged, repetitive or difficult to control (eg, status epilepticus, intractable epilepsy)
5	Death	Death	Death

#### Table 24. Cairo-bishop Clinical Tumor Lysis Syndrome Definition and Grading

Note. Laboratory TLS and at least 1 clinical complication will constitute clinical TLS.

ADL = activities of daily living, CHF = congestive heart failure, TLS = tumor lysis syndrome, ULN = upper limit of normal

a Not directly or probably attributable to therapeutic agent

b If no institutional ULN is specified, age/sex ULN creatinine may be defined as follows: > 1 to < 12 years of age, both male and female, 61.6 µmol/L; ≥ 12 to < 16 years, both male and female, 88 µmol/L; ≥ 16 years, female 105.6 µmol/L, male 114.4 µmol/L.

# Amendment 4

#### Title: A Phase 1, First-in-human, Open-Label Study Evaluating the Safety, Tolerability, Pharmacokinetics, and Efficacy of AMG 562 in Subjects With Relapsed / Refractory Diffuse Large B Cell Lymphoma, Mantle Cell Lymphoma, or Follicular Lymphoma

## Amgen Protocol Number (AMG 562) 20170533

Amendment Date: 07 August 2019

#### Rationale:

This amendment contains changes to the inclusion and exclusion criteria, to the definition of a dose limited toxicity (DLT) evaluable subject, and clarifications to the Schedule of Assessments that were made based on investigator and external advisor feedback to align with clinical standards and to address the urgent treatment need of the eligible patient population. The premedication schedule was adjusted based on the dose level review meeting (DLRM) outcome of Cohort 1 review. Operational changes and changes for clarification were made.

The following updates were made to the protocol amendment 3:

- Updated language regarding dose level review meeting decisions to recommendations to align with Amgen standard processes
- Adjustment of premedication schedule based on cohort 1 DLRM recommendation and allowing oral premedication with dexamethasone to add convenience
- Adjustment of reference dose for Bayesian Model based on the observation of a DLT at an early cohort
- Restructured inclusion criteria
- Allowing prior CD19 targeting therapies except prior CD19-directed CAR-T cell therapies
- Added biopsy to SOA for subjects with prior CD19 targeting treatment
- DLT evaluable subject definition updated
- Inclusion of treatment holiday
- Revisions to Disease Related Adverse Events collection guidelines as per ASAE Adoption Committee (AAC) guidance
- Adverse event (AE) management guideline changes to improve clarity and implementation at site level
- Revisions to adverse event management section to include information on hospitalizations for AEs and restart of IP following adverse events
- PK schedule adjustments to align with ECG timepoints to fulfill QT/QTc evaluation

• Biomarker language clarification for sample collection based on disease type and study part

• Typographical and grammatical errors corrected and aligned between sections

# Amendment 3

#### Title: A Phase 1, First-in-Human, Open-Label Study Evaluating the Safety, Tolerability, Pharmacokinetics, and Efficacy of AMG 562 in Subjects With Relapsed / Refractory Diffuse Large B Cell Lymphoma, Mantle Cell Lymphoma, or Follicular Lymphoma

### Amgen Protocol Number (AMG 562) 20170533

Amendment Date: 10 March 2019

#### Rationale:

This amendment contains changes that were requested by health authorities. In addition, it contains changes to the inclusion and exclusion criteria that were made based on investigator and external advisor feedback to align with clinical standards and to address the urgent treatment need of the eligible patient population.

The following updates were made to the protocol amendment 2:

- Language clarification:
  - Table 7. Grading and Management of Cytokine Release Syndrome.
  - Permanent discontinuation criteria for the occurrence of multiple Grade 2 or higher CRS events
  - o Concomitant therapies for infection treatment
- Washout period for check-point inhibitors and monoclonal antibody-based therapy was reduced based on the aggressive disease condition. A longer washout period is not feasible as per the standard of care.
- Excluded medication for infection treatment during DLT window unless discussed with Amgen medical monitor

# Amendment 2

## Title: A Phase 1, First-in-Human, Open-Label Study Evaluating the Safety, Tolerability, Pharmacokinetics, and Efficacy of AMG 562 in Subjects With Relapsed / Refractory Diffuse Large B Cell Lymphoma, Mantle Cell Lymphoma, or Follicular Lymphoma

# Amgen Protocol Number (AMG 562) 20170533

Amendment Date: 30 November 2018

# Rationale:

This amendment contains changes that were requested by health authorities and institutional review boards/ ethics committees. In addition, it contains changes to the inclusion and exclusion criteria that were made based on investigator and external advisor feedback.

The following updates were made to the protocol amendment 1:

- Typographical errors and inconsistencies between sections throughout the protocol were corrected
- Clarifications were made regarding schematics for weekly dosing to differentiate from Blincyto IP administration
- Background information was updated to reflect the recent approved therapy and benefit risk profile
- The step dosing triggers, conductance of DLRM clarified
- Premedication rules prior to IP administration updated based on HA feedback
- DLRT data review timelines for the Dose expansion clarified
- Table 8 to Table 11 (Schedule of Assessments) footnotes were updated to reflect the changes for VS and LTFU
- Several changes were made to inclusion/exclusion criteria at the request of health authorities or for streamlining purposes. The following inclusion/exclusion criteria were amended based on investigator and external advisor feedback:
- Legally Acceptable Representatives (LAR's) removed based on EC feedback
- Disease diagnosis clarified for DLBCL population
- Washout period reduced for prior exposure to Rituxan based on in vitro data
- Shortening of Hospitalization requirement only after substantial amendment clarified
- Table 7. Restart guidance for Grade 3 CRS for Grading and Management of CRS events updated
- LTFU visit requirements for onsite vs. remote visits clarified
- Table 13. List of analytes updated based on lab or site performing the evaluation
- Dose Level Review Team (DLRT) language clarified

- SEC (Self Evident Corrections) removed based on recent updates within organization to remove from all protocols
- Appendix I (PK samples timepoint collection clarified based on Start of Infusion)

# Amendment 1.0

Title: A Phase 1, First-in-Human, Open-Label Study Evaluating the Safety, Tolerability, Pharmacokinetics, and Efficacy of AMG 562 in Subjects With Relapsed / Refractory Diffuse Large B Cell Lymphoma, Mantle Cell Lymphoma, or Follicular Lymphoma

Amgen Protocol Number (AMG 562) 20170533

Amendment Date: 20 February 2018

### Rationale:

The following changes were made to the protocol dated 10 January 2018 to incorporate requested changes from FDA IND review, updates to PK, biomarker assessments and administrative clarifications:

- Updated dose regimens in the step-up dose exploration
- Modified to specify that the DLRT may prolong the dosing interval to every 2, 3 or 4 days.
- Updated to specify that enrollment in multiple subject cohorts will be staggered by 3 days.
- Updated to remove PPS and minocycline in the dose escalation portion of the protocol Section 3.1
- Revised to limit subsequent dose increases to no more than 2-fold after the occurrence of a DLT or ≥ 2 patients experiencing a Grade 2 AE.
- Revised to discontinue AMG 562 if the subject experiences Grade 3 or higher seizure on AMG 562.
- Revised to specify a Grade (eg, less than Grade 3 which resolves to Grade 2 or less) and a time to resolution for the DLT exceptions of headache and insomnia; and to include a time to resolution for the DLT exception of Grade 3 fever in Section 6.2.1.3.
- Updated to extend the DLT evaluation period to 28 days for single patient cohorts.
- Updated to remove the phrase "treatment related" from rules for transition from single subject to multiple subject cohorts.
- Updated to specify the requirement to submit a protocol amendment before administering doses > 1000 micrograms.
- Revised to clearly state that proposed changes to the DLT window will not include a shorter DLT evaluation period.
- Revise Table 7 to include the approved dose of 8 mg/kg of tocilizumab for treatment of CRS for patients.
- Revised Table 7 to state that subjects who experience Grade 3 CRS should receive steroids and tocilizumab.

- Revised to allow flexibility for use of additional medications eg, antihistamines and H2 blockers which could be administered prior to administration of AMG 562.
- Updated to remove dosing by bolus injection.
- Modified eligibility criteria to include patients with FL or MCL who have received three or more prior therapies.
- Updated Table 8 to Table 12 (Schedule of Assessments) to:
  - o remove PB for MRD assessments by NGS
  - o Removed some PK and biomarker assessment time points
- Updated protocol body and footnotes to reflect Table 8 to Table 12 revisions
- Corrected grammar errors throughout document.
- Updated Page numbers in Table of Contents.
